11.3 Statistical criteria of termination of trial

Formal statistical stopping rules will not be used in MYTHIC although the IDMC charter will specify guidelines for when the IDMC will alert the coordinating principal investigator or TMT to the need to discontinue the trial. These guidelines will be conservative to guard against premature discontinuation of the trial from early inspection of the data.

11.4 Planned analyses

Detailed methodology for summaries and statistical analyses of the data collected in MYTHIC will be documented in a separate statistical analysis plan. The statistical analysis plan will be finalized before database closure and will be under version control at the Department of Biostatistics, University of Zurich.

Analyses of sex differences are also planned.

11.4.1 Datasets to be analyzed, analysis populations

The full analysis set (FAS) will include **all patients who gave written informed consent and were enrolled**. Patients in the FAS will be analyzed according to the randomly assigned treatment, adhering to the intention-to-treat principle.

The per protocol set (PPS) will include all patients from the FAS who are **Mp PCR-positive** (section 6.1, Table 5) and who are sufficiently compliant to treatment ($\geq 80\%$ of the medication used).

The strict per protocol set (strict PPS) will include all patients from the PPS who additionally have **confirmed Mp infection by IgM ASC ELISpot assay** (section 6.1, Table 5).

Patients in the PPS and strict PPS will be analyzed according to the received treatment (in case there are any deviations from the randomized treatment).

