Rationale: The resolution of all VS abnormalities has been proposed as an important primary endpoint for antibiotic trials in childhood pneumonia by the IDSA [62]. In contrast to adults, severe morbidity and mortality from CAP is minimal in children, particularly for *Mp* CAP (section 3.5 and 3.7). Previous trials on macrolides for *Mp* CAP have mainly focused on fever duration as a key endpoint [31, 32]. In the myCAP study, the median body temperature (T) at presentation among myCAP patients was 39.1°C (IQR, 39.0-39.7), and the clinical diagnosis of CAP based on fever and tachypnea could be radiologically confirmed in 98% of the cases [43]. On room air, 17% *Mp* CAP patients had an SpO₂<93% and required additional oxygen supply. The median fever duration for *Mp* CAP children was 2 days. There were no statistically significant differences between patients with or without antibiotic treatment for *Mp* [43]. Lu et al. [63] observed a mean fever duration of 5 days (no statistically significant differences between patients treated with macrolides or placebo). To conclude, this study will use VS measurements taken at the timepoint before randomization as baseline measurements. The VS measurements will be followed up until normalization of VS to reference values. We expect a rate of <1% of patients' VS not normalizing within a 28-day FUP. In agreement with the IDSA considerations [62], an assessment of the time to VS normalization (T, RR, HR, SpO₂) has been selected to be of main interest for MYTHIC.

1.2: CAP-related change in patient care status within 28 days (safety)

Defined as any change in patient care status from an ambulatory to hospitalized setting (admission or re-admission), or from a hospitalized on general ward to an ICU setting (ICU transfer).

Specific measurement: Incidence of (re-)admission to hospital or transfer to the ICU.

Analysis metric: Final value.

Method of aggregation: Proportion.

Time point: Within 28 days after randomization.

Rationale: We expect the placebo to be non-inferior to macrolides treatment regarding a CAP-related change in patient care status. This non-inferiority will be assessed by the incidence of (re-)admission to

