6.3 Unblinding procedures (code break)

In the MYTHIC, no situations needing emergency unblinding are foreseen. AEs caused by drug toxicity and needing discontinuation of the drug are expected to be extremely rare when administering azithromycin in regular doses and for 5 days. The acute toxicity of a one-off azithromycin overdose is very limited. There is no specific antidote and management is symptomatic. Allergic reactions to any of the ingredients of the formulation can occur. However, these are extremely rare. In situations where an allergic reaction due to trial treatment is suspected, and further regimen doses are due, trial treatment is to be discontinued. The following criteria for discontinuation or modification (Table 6) guarantee safety in MYTHIC without the necessity of unblinding the IMP:

Table 6. Criteria and procedures for discontinuation or modification of the IMP.

Discontinuation criteria:	Modification criteria:

 Any change in the patient's condition that justifies the discontinuation of the IMP (e.g., need for ICU transfer). Unacceptable toxicity or AE (according to the prescribing information). Use of a medication with a known major drug interaction with azithromycin. Withdrawal of informed consent for IMP by patient/parent. 	
Ambulatory patients:
 
 Need for hospital admission. 
Hospitalized patients:
 
 Failure to maintain oxygen saturation $\geq 90\%$ with FIO_2 100%. Oxygen saturation $< 90\%$ for $> 48h$. Clinical features of severe respiratory distress/exhaustion and/or shock/sepsis.
Procedures:	Procedures:

 Stop IMP 	
 Treatment modification with antibiotics against atypical pathogens* and/or Switch to standard of care**

Important note: Decision about additional treatment with beta-lactams (such as amoxicillin) to avoid potential non-treatment of co-infecting bacterial pathogens (e.g., Streptococcus pneumoniae) in study patients will be made by the treating physician and will not be influenced by local investigators or TMT.*/**
	

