8.6 Trial-specific preventive measures

In situations with a clinical indication for treatment modification as defined in section 6.3 (Table 6, “**Modification criteria**”), the IMP may be modified with another antibiotic against atypical pathogens, such as clarithromycin (as another potent macrolide) or doxycycline in children ≥8 years of age (also as treatment option for infections with MRMP) [9]. This situation is expected to be rare and is unlikely to impact the trial results. Decision-making by the local investigators and the TMT will be possible and safe in such situation without the need to unblind the treatment allocation. However, the use of treatment modification will be recorded in secuTrial®. Patients should remain in the study for FUP and should continue to follow the assessment schedule.

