11.4.2 Primary analysis

To assess the non-inferiority of placebo vs. azithromycin regarding the co-primary endpoint **time to**

normalization of VS, we will estimate the hazard ratio of placebo vs. azithromycin with a two-sided 97.5% CI using a Cox proportional hazards model on the PPS (defined in section 11.4.1). Non-inferiority of placebo will be declared if the lower limit of the CI will be larger than the non-inferiority margin (i.e., the whole CI lies entirely above the margin).

To assess the non-inferiority of placebo vs. macrolide regarding the co-primary endpoint **CAP-related change in patient care status**, we will estimate the absolute risk difference ($ARD = risk_{azithromycin} - risk_{placebo}$) with a two-sided 97.5% CI on the PPS. Non-inferiority of placebo will be declared if the lower limit of the CI will be larger than the non-inferiority margin (i.e., the whole CI lies entirely above the margin).

The two non-inferiority tests will be performed and interpreted independently (of each other) and the trial considered successful if non-inferiority can be shown for at least one of the primary outcomes. Should the resulting CIs exclude the reference value for no difference (1 for hazard ratio, 0 for ARD), the result can be interpreted as superiority of either treatment [88].

To complement the main analyses above, the following sensitivity and additional analyses are planned:

- We consider the **PPS as the main set for showing non-inferiority** (section 6.1, Table 5), and the sample size calculation was also done with regard to the PPS (section 11.2). In addition, we will also test non-inferiority in the strict PPS and the FAS. Since the three analysis sets (FAS, PPS, and strict PPS) differ considerably in size and composition (section 6.1, Table 5), we will consider the PPS as the relevant set for concluding non-inferiority, but we will discuss differences in the conclusions based on the different sets. For a robust interpretation of the non-inferiority test these analyses should lead to similar conclusions as the main analysis [87].
- For CAP-related change in patient care status, we will present the 2×2 table of events per treatment arm and an unadjusted odds ratio (OR) estimate for all three analysis sets.
- For time to VS normalization, we will plot Kaplan-Meier curves and estimate median time-to-event by trial arm.

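### A child whose study drug ends before the fourth dose because of a co-primary safety event, such as ICU transfer, leaves the set that decides the safety test

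*Protocol*

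**What the plan says.** All references are to the protocol.

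- **Primary set.** Section 11.4.1 admits to the PPS children who are PCR-positive "and who are sufficiently compliant to treatment", with the threshold set at 80% or more of the medication used. No exception is given.
- **Its role.** Section 11.4.2 states: "we will consider the PPS as the relevant set for concluding non-inferiority". Tests in the full analysis set (FAS) and the strict PPS are listed as sensitivity and additional analyses, and differences between sets are to be discussed.
- **Outcome 1.2.** Section 5.1 counts two kinds of event over 28 days. The first is a child managed at home who is admitted or readmitted. The second is given as "or from a hospitalized on general ward to an ICU setting (ICU transfer").
- **Stopping.** Section 6.3, Table 6, lists among the criteria for stopping the IMP any change in condition that "justifies the discontinuation of the IMP (e.g., need for ICU transfer"). Section 7.4 repeats this.
- **Modification.** In the same table, hospital admission of an ambulatory child and the listed signs of deterioration in hospitalized children are modification criteria. They lead to antibiotics against atypical pathogens and/or standard of care. A footnote to the table asks that the IMP be continued for all five days where possible. Section 8.6 allows the IMP to be modified with another antibiotic in these situations and comments: "This situation is expected to be rare and is unlikely to impact the trial results".

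**The concern.** Membership of the decisive set depends on something measured after randomization that the endpoint itself can cause. A child transferred to ICU on day 2 or 3 has an outcome 1.2 event. If the IMP is stopped as Table 6 foresees, the child falls below 80% and is removed together with the event. A child admitted from home is removed in the same way if the IMP is in fact replaced under section 8.6 before the fourth dose.

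Removing events shrinks both risks and so shrinks their difference. In a trial that aims to show placebo is not worse, that is the favourable direction, and no imbalance in removal between arms is needed. Section 11.4.2 calls the trial successful if either co-primary test succeeds, so a biased safety test could carry the conclusion alone. With a planned risk of 5%, only about 16 events are expected in 322 children (322 × 0.05 = 16.1), so a few lost events matter.

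**Working it through.** **1. The plan's own figure.** Section 11.2 gives risk 5% in both arms, margin 7.5 points, one-sided alpha 1.25% and power 80%.

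n per arm = (2.2414 + 0.8416)² × 2 × 0.05 × 0.95 / 0.075² = 160.5, so 161 per arm and 322 in total, as stated. 322 / (1 − 0.145) = 376.6, against the stated 376 (rounding).

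**2. What 80% means in doses.** The regimen in section 8.2.1 is two units on day 1 and one unit on each of days 2 to 5, six units in all. Cumulative shares are 2/6, 3/6, 4/6, 5/6 and 6/6, that is 33%, 50%, 67%, 83% and 100%. Table 7 volumes give the same in every weight band except 15 to under 20 kg (32%, 49%, 66%, 83%, 100%). Counted by doses, four of five is exactly 80%. Either way, a child is excluded if the IMP ends before the fourth dose and meets the threshold once the fourth dose is taken.

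**3. Effect on the test.** Let f be the share of outcome 1.2 events that end the IMP before the fourth dose, taken as equal in both arms. The documents do not give f, so it is an assumption shown over a range.

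- Risk left in the PPS: p(1 − f) / (1 − pf)
- Children left per arm: 161(1 − pf)
- Probability of declaring non-inferiority: Φ((0.075 − difference) / SE − 2.2414)

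True risks are set at the margin: 5% azithromycin, 12.5% placebo. Example for f = 25%: azithromycin 0.0375 / 0.9875 = 3.80%; placebo 0.09375 / 0.96875 = 9.68%; difference 5.88 points; SE 2.81 points; Φ(0.576 − 2.241) = 4.8%.

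| f | PPS risks (azithromycin, placebo) | Difference (points) | False non-inferiority, normal approximation | Exact binomial, Wald interval |
|---|---|---|---|---|
| 0 | 5.0%, 12.5% | 7.5 | 1.25% | 1.6% |
| 5% | 4.8%, 12.0% | 7.2 | 1.6% | 2.1% |
| 10% | 4.5%, 11.4% | 6.9 | 2.1% | 2.8% |
| 25% | 3.8%, 9.7% | 5.9 | 4.8% | 6.4% |
| 50% | 2.6%, 6.7% | 4.1 | 21% | 24% |

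The exact column starts at 1.6%, so part of its excess over 1.25% comes from the Wald interval and not from the exclusion.

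**4. Effect on the margin.** Section 11.2 defends the margin because the implied maximum placebo risk, 12.5%, lies below an acceptable failure rate of 13.5%. With azithromycin at 5%, the true placebo risk at which the PPS difference equals 7.5 points solves p = t / (1 − f + tf), where t is the azithromycin PPS risk plus 0.075. At f = 25%, t = 0.1130 and p = 14.5%. At f = 50%, t = 0.1006 and p = 18.3%. Both exceed 13.5%.

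**The case against.** A reader might infer that the safety analysis loses its events in general, or that Table 6 orders the drug stopped at any deterioration. The documents do not support this. Admission and the listed deterioration signs are modification criteria, and the footnote asks for the IMP to continue where possible. Section 3.5 reports that only 32% of children with this pneumonia were hospitalized. If that holds here, most children would first meet outcome 1.2 through admission, for which no stop is ordered. Outcome 1.2 also runs for 28 days, and events from the fourth dose onwards cause no exclusion. All of this stands, and it limits the loss to events that actually end the IMP early.

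Very large inflation figures are not supported either. At f = 75% and the margin risks, the average loss would be 0.75 × (5% + 12.5%) / 2 = 6.6% of children for this reason alone. That exceeds the 5% that section 11.2 allows for all loss to follow-up and insufficient compliance.

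The FAS test and the 2×2 tables for all three sets would show the removed events, and section 11.4.2 says the sets should lead to similar conclusions. This gives visibility, but the PPS still decides, and a failed FAS test does not block the claim.

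Section 11.4 leaves detailed methods to the statistical analysis plan. However, the protocol itself fixes the threshold, without qualification, and the decisive role of the set. A plan that follows it literally inherits the bias.

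A reader might extend the point to the as-treated rule for the PPS, or to later vital-sign normalization being credited to placebo after added antibiotics. No effect of the as-treated rule is shown under blinded kit allocation. How to treat added antibiotics for outcome 1.1 is a choice of estimand, not an error established here.

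**Conclusion.** The point holds in a limited form. The primary set for the safety test excludes children because of a safety event whenever that event ends the IMP before the fourth dose. ICU transfer is the clear case, since the protocol names it both as endpoint and as a reason to stop. Admission is a possible case, through replacement of the IMP under section 8.6.

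The direction is certain under equal removal in both arms: towards non-inferiority of placebo. The size is not known. Against a nominal 1.25%, false non-inferiority is about 1.6% to 2.1% if 5% to 10% of events are lost, 4.8% at 25% and 21% at 50%. These figures assume true risks at the margin, 161 PCR-positive and otherwise compliant children per arm before this exclusion, and the same f in both arms. With so few events expected, the remark in section 8.6 that modification is unlikely to affect the results is not secured by anything in the protocol. The wording should be corrected before the data are analysed.

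**What to change.** In section 11.4.1, state that compliance is judged only on doses due before a co-primary event or a Table 6 stop or modification, so that no child leaves the PPS because of such an event. Alternatively, base outcome 1.2 on all randomised PCR-positive children, analysed as randomised. Keep the unqualified 80% set as a sensitivity analysis, and carry the change into section 11.4.2.

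Reconcile Table 6 with its footnotes (section 6.3), section 8.6 and section 11.4.1 on how a stopped or replaced IMP counts towards compliance. No clinical rule needs to change for this.

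Cost: a few children with incomplete dosing stay in the primary set. Table 6 also lists stops for toxicity, interacting medication and withdrawal of consent for the IMP, so the wording should say whether those are treated alike. No new data are needed, because sections 8.6 and 9.3 already keep such children in follow-up to day 28. The planned 322 evaluable and 376 enrolled are unchanged.

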11.4.2 Primary analysis

To assess the non-inferiority of placebo vs. azithromycin regarding the co-primary endpoint **time to**

normalization of VS, we will estimate the hazard ratio of placebo vs. azithromycin with a two-sided 97.5% CI using a Cox proportional hazards model on the PPS (defined in section 11.4.1). Non-inferiority of placebo will be declared if the lower limit of the CI will be larger than the non-inferiority margin (i.e., the whole CI lies entirely above the margin).

To assess the non-inferiority of placebo vs. macrolide regarding the co-primary endpoint **CAP-related change in patient care status**, we will estimate the absolute risk difference ($ARD = risk_{azithromycin} - risk_{placebo}$) with a two-sided 97.5% CI on the PPS. Non-inferiority of placebo will be declared if the lower limit of the CI will be larger than the non-inferiority margin (i.e., the whole CI lies entirely above the margin).

The two non-inferiority tests will be performed and interpreted independently (of each other) and the trial considered successful if non-inferiority can be shown for at least one of the primary outcomes. Should the resulting CIs exclude the reference value for no difference (1 for hazard ratio, 0 for ARD), the result can be interpreted as superiority of either treatment [88].

To complement the main analyses above, the following sensitivity and additional analyses are planned:

- We consider the **PPS as the main set for showing non-inferiority** (section 6.1, Table 5), and the sample size calculation was also done with regard to the PPS (section 11.2). In addition, we will also test non-inferiority in the strict PPS and the FAS. Since the three analysis sets (FAS, PPS, and strict PPS) differ considerably in size and composition (section 6.1, Table 5), we will consider the PPS as the relevant set for concluding non-inferiority, but we will discuss differences in the conclusions based on the different sets. For a robust interpretation of the non-inferiority test these analyses should lead to similar conclusions as the main analysis [87].
- For CAP-related change in patient care status, we will present the 2×2 table of events per treatment arm and an unadjusted odds ratio (OR) estimate for all three analysis sets.
- For time to VS normalization, we will plot Kaplan-Meier curves and estimate median time-to-event by trial arm.
- Covariate-adjusted analyses will be performed for both endpoints and all analysis sets, considering all variables used in the minimization for treatment allocation (section 6.2.1). For time to VS normalization, a mixed-effects Cox proportional hazards model with a random intercept per center will be used [88]. For change in patient care status, a generalized linear mixed-effects model will be used. Explanatory variables in both models are treatment (placebo vs. azithromycin), age (continuous), patient care status (ambulatory vs. hospitalized), and prodromal symptom duration (continuous).

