Statistical considerations:	
Multiplicity with two co-primary endpoints was handled using the “at least one” success criterion: We estimated the sample size for both co-primary endpoints for a one-sided significance level of 1.25% and a power of 80%, and use the larger of the two sample sizes for the trial. This assures a minimum power of 80% to reject at least one null hypothesis.
 
The co-primary endpoint time to normalization of all VS is considered as a time-to-event endpoint. The sample size was estimated assuming an overall event rate of 99% and a hazard ratio of 1 for placebo vs. macrolide (a hazard ratio <1 would indicate longer duration with placebo than with macrolide). The sample size was estimated to show the non-inferiority of placebo vs. macrolide in Mp PCR-positive patients using a non-inferiority margin of 0.7 for the hazard ratio. Considering a drop-out rate of 14.5%, 354 patients should be recruited for the intervention phase of this study (302 evaluable patients).
 
For the co-primary endpoint CAP-related change in patient care status (binary) we expect an absolute risk of 5% in both trial arms and thus an absolute risk difference (ARD, $risk_{macrolide} - risk_{placebo}$) of 0 between the two arms. An ARD <0 would indicate a higher risk with placebo than macrolide. The sample size was estimated to show the non-inferiority of placebo vs. macrolide in Mp PCR-positive patients, using a non-inferiority margin of -7.5% for the ARD. Considering a drop-out rate of 14.5%, 376 patients should be recruited for the intervention phase of this study (322 evaluable patients).

GCP statement:	
This study will be conducted in compliance with the protocol, the current version of the Declaration of Helsinki, ICH-GCP, as well as all national legal and regulatory requirements.

ABBREVIATIONS

AE	Adverse event
AESI	Adverse event of special interest
AMR	Antimicrobial resistance
AR	Adverse reaction
ARD	Absolute risk difference
ASC	Antibody-secreting cell
ASR	Annual safety report
BASEC	Business Administration System for Ethical Committees (https://submissions.swissethics.ch/en/)
BTS	British Thoracic Society
CA	Competent authority (e.g., Swissmedic)
CAP	Community-acquired pneumonia
CEC	Competent ethics committee
CI	Confidence interval
ClinO	Ordinance on Clinical Trials in Human Research (in German: KlinV, in French: OClin, in Italian: OSRUm)
CTCAE	Common terminology criteria for adverse events

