4.2 Co-primary objectives

This study aims to show in ambulatory and hospitalized children aged 3-17 years with *Mp* CAP that treatment with placebo is non-inferior to treatment with azithromycin in terms of (1.1) efficacy and (1.2) safety:

1.1: Efficacy: Time to normalization of all VS, including body temperature (T), respiratory rate (RR), heart rate (HR), and saturation of peripheral oxygen (SpO₂).

Hypothesis: The administration of a placebo in pediatric *Mp* CAP will be non-inferior with respect to the duration of VS abnormalities compared to a 5-day azithromycin regimen.

1.2: Safety: CAP-related change in patient care status, such as (re-)admission or ICU transfer, within 28 days after the index episode.

Hypothesis: The administration of a placebo in pediatric *Mp* CAP will be non-inferior with respect to the CAP-related change in patient care status compared to a 5-day azithromycin regimen.

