11.2 Determination of sample size

Sample size calculations were done with regard to the per protocol set (PPS), which includes patients who are positive for *Mp* by PCR (section 6.1, Table 5). To handle multiplicity with two co-primary endpoints, we apply the “at least one” success criterion [83]: We estimated the sample size for both co-primary endpoints at a one-sided significance level (α) of 1.25% (which corresponds to two-sided 97.5% confidence intervals [CI]) and a power of 80% ($\beta=20\%$), and use the larger of the two sample sizes for the trial. This assures a minimum power of 80% to reject at least one null hypothesis.

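### Testing each co-primary at a fixed one-sided 1.25% leaves alpha unused (about 66% power to show both, against about 77% with Holm), and one verdict of success covers either endpoint

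*Protocol*

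**What the plan says.** The objective in section 4.2 is to show that "treatment with placebo is non-inferior to treatment with azithromycin in terms of (1.1) efficacy and (1.2) safety", followed by a separate hypothesis for each endpoint. Endpoint 1.1 is time to normalization of all vital signs; endpoint 1.2 is CAP-related change in care status within 28 days.

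Section 11.2 sizes both endpoints "at a one-sided significance level (α) of 1.25"%, with 80% power each, and will "use the larger of the two sample sizes for the trial". Its only power statement for the pair is: "This assures a minimum power of 80% to reject at least one null hypothesis".

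Section 11.4.2 compares a two-sided 97.5% confidence interval with each margin in the per protocol set (PPS), interprets the two tests independently of each other, and has "the trial considered successful if non-inferiority can be shown for at least one of the primary outcomes". If an interval excludes no difference, "the result can be interpreted as superiority of either treatment". The same section adds analyses in the full analysis set (FAS) and the strict PPS, and regards the PPS as the relevant set for concluding non-inferiority.

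Section 11.4.1 defines the PPS as PCR-positive patients who used at least 80% of the medication, analysed by treatment received.

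**The concern.** There are three linked issues.

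- The objective names efficacy and safety together, while the decision rule attaches one unqualified verdict of success to either endpoint. The plan does not say what overall conclusion follows if one is met and the other is not.
- Having split alpha equally, the plan holds both tests at 1.25% whatever happens. After one rejection, Holm's step-down would allow the other endpoint to be tested at 2.5% with no increase in family-wise error. The power for showing both is never stated, so a reader cannot see what this costs.
- Superiority may be read from intervals computed in a set that is partly selected, and partly regrouped, after randomisation.

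At stake is the chance of supporting the full claim on efficacy and safety, and how clearly a mixed result can be read.

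**Working it through.** **Inputs.** From section 11.2: one-sided alpha 1.25%; power 80%; hazard ratio 1 with margin 0.7; event rate 99%; risk 5% in both arms with margin 7.5 percentage points; drop-out 14.5%. Allocation is 1:1 (section 6.2.1). The documents give no correlation between the two test statistics. I assume 0 and show results up to 0.8.

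**Reproducing the plan's sizes.** With z = 2.2414 and 0.8416, the squared sum is 3.0830² = 9.505.

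- Vital signs: 9.505 / (0.25 × 0.3567²) = 298.9 events; divided by 0.99 this is 301.9, so 302. This agrees.
- Care status: 9.505 × 0.095 / 0.075² = 160.5, so 161 per arm and 322 in total. This agrees.
- Enrolled: 302/0.855 = 353.2, so 354, which agrees. 322/0.855 = 376.6, against 376 stated, a rounding difference of no consequence.

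**Power of each test at 322 evaluable.**

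- Vital signs: standardised distance √(0.99 × 322/4) × 0.3567 = 3.184. Power is Φ(3.184 − 2.241) = 82.7% at 1.25%, and Φ(3.184 − 1.960) = 89.0% at 2.5%.
- Care status: 0.075 / √(0.095/161) = 3.088. Power is Φ(3.088 − 2.241) = 80.1% at 1.25%, and Φ(3.088 − 1.960) = 87.0% at 2.5%.

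**Power for the pair under independence.**

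- At least one, as planned: 1 − 0.173 × 0.199 = 96.6%.
- Both, as planned: 0.8271 × 0.8013 = 66.3%.
- Both under Holm (both p-values at most 2.5%, the smaller at most 1.25%): 0.8271 × 0.8703 + 0.8896 × 0.8013 − 0.6627 = 77.0%.
- Both required, each at 2.5%: 0.8896 × 0.8703 = 77.4%.

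**Sensitivity to correlation (bivariate normal), power to show both.**

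| Correlation | As planned | Holm | Both required at 2.5% |
|---|---|---|---|
| 0 | 66.3% | 77.0% | 77.4% |
| 0.3 | 68.7% | 78.3% | 78.9% |
| 0.5 | 70.6% | 79.5% | 80.2% |
| 0.8 | 74.6% | 81.8% | 82.9% |

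Holm gains about 7 to 11 percentage points throughout. Power for at least one is unchanged by Holm, because the first step still needs a p-value of at most 1.25%.

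**The set used for superiority.** The PCR criterion uses the day-1 swab (sections 6.1 and 9.3.2) and is a baseline characteristic. The compliance rule and the grouping by treatment received are not. Compliance can also be tied to outcome: Table 6 gives need for ICU transfer as an example of a reason to stop study medication. Under the schedule in section 8.2.1, a child stopped before the day-4 dose has taken 10 + 5 + 5 = 20 of 30 mg/kg, or 67%, and falls below the 80% threshold.

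**The case against.** The protocol makes no statistical error here. The at-least-one criterion is deliberate, cited and stated consistently; two tests at 1.25% control family-wise error at 2.5%; and the 80% claim is true and conservative. Power for both endpoints was never a stated target, so 66% is not a shortfall against the plan. All of this stands.

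A reader might infer that placebo can win while failing on safety. With a true hazard ratio of 1 and a true placebo risk at the 12.5% limit, the trial would indeed be called successful about 83% of the time. That is not an error rate: it is essentially the 82.7% power for vital signs, where non-inferiority is then truly present, and safety non-inferiority is falsely declared in only 1.25%. Section 11.4.2 declares results endpoint by endpoint and nowhere says that one success justifies withholding macrolides. Care status is also a named safety outcome (section 5.4), and the data monitoring committee reviews safety at one third and two thirds of patients (section 11.4.4). What remains is that success is left unqualified when only one endpoint is met.

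A reader might also infer that a superiority statement from the PPS has no basis in randomisation. That goes too far. Most of the planned loss (10%, against 5% for loss to follow-up or poor compliance) comes from the baseline PCR criterion, and the FAS is analysed alongside.

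Finally, Holm is not entirely free. The decision rule is based on confidence intervals, and Holm makes the second interval's level depend on the first result. A 97.5% interval paired with a 95% interval also loses simultaneous coverage.

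**Conclusion.** The point holds as an improvement that should be made, not as a fault that invalidates the design. With 322 evaluable patients and the plan's own assumptions, fixed 1.25% tests give about 66% power to show both endpoints under independence, and 69% to 75% at correlations of 0.3 to 0.8. Holm gives about 77%, and 78% to 82%, at the same family-wise error. The figures rest on the normal approximations that reproduce the plan's sample sizes. The correlation is an assumption, but the gain persists over the whole range examined.

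Two smaller matters also stand: the meaning of success when only one endpoint is met is not defined, and superiority should not rest on a compliance-selected, as-treated set.

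**What to change.** 1. Keep the at-least-one criterion but use Holm: test the smaller p-value at one-sided 1.25% and, if that is rejected, the other at 2.5%. Reword the interval rule to match: a 97.5% interval at the first step, a 95% interval for the other endpoint only after a rejection. N is unchanged.
2. State that meeting one endpoint supports a conclusion about that endpoint only, and that overall non-inferiority on efficacy and safety is concluded only if both are met. This is wording only. Making both the formal success criterion, each at one-sided 2.5%, is optional. Under independence it gives about 77% at this N, below the protocol's 80% standard; reaching 80% would take 338 evaluable, or 338/0.855 = 395.3, so 396 enrolled against 376.
3. Base any superiority statement on the FAS as randomised. Because Holm passes the first endpoint's alpha to the second, label superiority as supportive or test it only after both non-inferiority nulls are rejected.

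These changes should be made by amendment before unblinding, so that the choice cannot look data-driven.
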